8.10.1.1 Rescreening

NOTE: As of Amendment 011-03, this section is no longer applicable.

Participants may be rescreened after initially failing to meet inclusion/exclusion criteria. Results of assessments during the original screening period are acceptable in lieu of repeat screening tests if obtained within the specified time frame and the corresponding criteria are met. Rescreened participants will retain their original screening numbers

8.10.2 Initial Treatment

Visit requirements are outlined in the SoA (Section 1.3). Assessments/procedures are to be performed prior to administration of study intervention.

8.10.2.1 Telephone Contact or Visit

NOTE: As of Amendment 011-03, this section is no longer applicable.

A telephone contact or visit will be conducted on Cycle 1 Day 8 to assess participants for development of early toxicity, as outlined in the SoA (Section 1.3.1).

8.10.3 Second Course Treatment

Note: As of Amendment 011-04, Second Course will no longer be offered. Any participant receiving Second Course treatment prior to the initiation of Amendment 011-04 will be able to complete treatment as planned.

All participants who have completed the first course may be eligible for up to an additional 17 cycles of pembrolizumab if there is investigator-determined progressive disease by RECIST 1.1 after initial treatment or first course has been completed or stopped for confirmed CR. This retreatment is the Second Course of this study.

Participants may enter the Second Course if all of the following criteria are met:

1. The participant received pembrolizumab, determined on unblinding if applicable
2. No new anticancer treatment was administered after the last dose of study intervention
3. The participant meets all of the inclusion criteria and none of the exclusion criteria
4. The study is ongoing

Treatment may continue until a discontinuation criterion is met (Section 7.1).

Second Course visit requirements are outlined in the SoA (Section 1.3.2). Specific procedure-related details are provided in Sections 8.1 and 8.2.

An objective response or disease progression occurring during the Second Course phase will not be counted as an event for the primary analysis of either endpoint in this study.

8.10.4 Discontinued Participants Continuing to be Monitored in the Study

The discontinuation visit should take place at the time study intervention is discontinued for any reason. If the discontinuation visit takes place 30 days from the last dose of study intervention, at the time of the mandatory safety follow-up visit, the safety visit is not required. All procedures required at the discontinuation visit and at the 30-day safety follow-up visit should be performed.

8.10.5 Post-treatment Visits

8.10.5.1 Safety Follow-up Visit

The mandatory safety follow-up visit should take place approximately 30 days after the last dose of study intervention or before initiation of new anticancer treatment, whichever comes first.

Participants who are eligible for Second Course Treatment may have up to 2 safety follow up visits, 1 after initial treatment and 1 after Second Course treatment.

8.10.5.2 Efficacy Follow-up Visits

Note: As of Amendment 011-04, this section is no longer applicable. Participants in Efficacy Follow-up prior to the initiation of Amendment 011-04 will stop efficacy assessments and be discontinued from the study. AEs and spontaneously reported pregnancies will be reported and followed as described under Section 8.4.

Participants who discontinue study intervention for a reason other than PD will move into the follow-up phase and should be assessed as outlined in the SoA (Section 1.3) to monitor disease status. Every effort should be made to collect information regarding disease status until the start of new anticancer therapy, PD, death, end of study, or the participant begins retreatment as detailed in Section 8.10.3. Information regarding poststudy anticancer treatment will be collected if new treatment is initiated.

Participants who are eligible for retreatment according to the criteria in Section 8.10.3 may move from follow-up to the Second Course phase if they experience PD. Details are provided in the SoA (Section 1.3.2).

8.10.6 Survival Follow-up

Note: As of Amendment 011-04, this section is no longer applicable. Participants in Survival Follow-up prior to initiation of Amendment 011-04 are considered to have completed the study and should have a final survival contact; these participants will no longer be contacted for survival information. AEs and spontaneously reported pregnancies will be reported and followed as described under Section 8.4.

Participants who experience confirmed disease progression or start a new anticancer therapy, will move into the Survival Follow-up phase and should be contacted approximately every 12 weeks to assess for survival status until death, withdrawal of consent, or the end of the study, whichever occurs first.

8.10.7 Survival Status

Note: As of Amendment 011-04, this section is no longer applicable. Survival data is no longer being collected.

To ensure that current and complete survival data are available at the time of database locks, updated survival data may be requested during the study by the Sponsor. For example, updated survival data may be requested prior to, but not limited to, an external DMC review or an interim or final analysis. Upon Sponsor notification, all participants who do not or will not have a scheduled study visit or study contact during the Sponsor-defined period will be contacted for their survival status.

9 STATISTICAL ANALYSIS PLAN

NOTE: Efficacy data and non-binding futility boundaries were provided to the eDMC, in addition to safety analyses, to evaluate the benefit/risk ratio of the experimental arm relative to the control arm for LEAP-011 (data cutoff: 26-APR-2021). The interim efficacy data indicated that although the study did not meet non-binding futility boundaries for any of the analyzed endpoints, improvements of outcomes in favor of the combination are unlikely to be as high as initially hypothesized. Based upon these data and the recommendation of the eDMC, Amendment 011-03 was implemented to unblind the study and remove lenvatinib and matching placebo from the treatment arms. The prespecified interim and final analyses of the study described in the statistical analysis plan (SAP) will not be performed. Selected analyses of safety endpoints will be performed at the end of the study; there will be no further analyses of efficacy or ePRO endpoints.

This section outlines the statistical analysis strategy and procedures for the study. If, after the study has begun, but before any unblinding/final database lock, changes are made to primary and/or key secondary hypotheses, or the statistical methods related to those hypotheses, then the protocol will be amended (consistent with ICH Guideline E9). Changes to exploratory or other nonconfirmatory analyses made after the protocol has been finalized, but before unblinding/final database lock, will be documented in a supplemental statistical analysis plan (sSAP) and referenced in the clinical study report (CSR) for the study. Post hoc exploratory analyses will be clearly identified in the CSR. Other planned analyses (ie, those specific to PK/ADA data and PROs) will be documented in separate analysis plans.

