Indication	Advanced/unresectable or metastatic urothelial carcinoma
Population	Cisplatin-ineligible participants with CPS ≥ 10 , or participants ineligible for any platinum-containing chemotherapy regardless of CPS, with advanced/unresectable or metastatic UC
Study Type	Interventional
Intervention Model	
Parallel
 
This is a multi-site study.
 
Note: As of Amendment 011-03, all participants will be unblinded and receive study treatment with pembrolizumab monotherapy.

Type of Control	
Placebo
 
Note: As of Amendment 011-03, placebo has been removed.

Study Blinding	
Double-blind with in-house blinding
 
Note: As of Amendment 011-03, the study is unblinded, open-label.

Masking	
Participant or Subject
 
Investigator
 
Sponsor
 
Note: As of Amendment 011-03, the study is unblinded, open-label.

Estimated Duration of Study	The Sponsor estimates that the study will require approximately 5 years from the time the first participant signs the informed consent until the last participant's last study-related contact or visit.
-----------------------------	----------------------------------------------------------------------------------------------------------------------------------------------------------------------------------------------------------

Number of Participants:

Approximately 694 participants will be randomized. As of Amendment 011-03, approximately 487 participants have been randomized and no additional participants will be randomized.

Intervention Groups and Duration:

Intervention Groups	NOTE: As of Amendment 011-03, lenvatinib and placebo are removed. All participants remaining in the study will receive open-label pembrolizumab only. 
  
 Intervention Group Name	Drug	Dose Strength	Dose Frequency	Route of Admin	Treatment Period	Use	
   
 Arm 1 and 2	Pembrolizumab	200 mg	Q3W	IV Infusion	~2 years (initial treatment) ~1 year (Second Course)	Background Treatment	
  
 
Abbreviations: Admin = administration; IV = intravenous; Q3W = every 3 weeks.
							Intervention Group Name	Drug	Dose Strength	Dose Frequency	Route of Admin	Treatment Period	Use	Arm 1 and 2	Pembrolizumab	200 mg	Q3W	IV Infusion	~2 years (initial treatment) ~1 year (Second Course)	Background Treatment

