4.2.2 Rationale for the Use of Placebo

NOTE: As of Amendment 011-03, this section is no longer applicable.

The use of a placebo in combination with pembrolizumab will ensure the objectivity of the local investigators' treatment decision and AE causality assessments.

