6.1 Study Intervention(s) Administered

NOTE: As of Amendment 011-03, only pembrolizumab will be administered. Other study treatments (prior to this amendment) have been deleted. The study intervention(s) to be used in this study are outlined in [Table 2](#).

Table 2 Study Interventions

Arm Name	Arm Type	Intervention Name	Type	Dose Formulation	Unit Dose Strength(s)	Dosage Level(s)	Route of Administration	Treatment Period	Use	IMP/ NIMP	Sourcing
Arm 1 and 2	Experimental	Pembrolizumab	Biological/ Vaccine	Solution for Infusion	25 mg/mL	200 mg	IV Infusion	Q3W	Background Treatment	IMP	Central

Abbreviations: IV = intravenous; Q3W = every 3 weeks.

Definition of Investigational Medicinal Product (IMP) and Non-Investigational Medicinal Product (NIMP) is based on guidance issued by the European Commission. Regional and/or Country differences of the definition of IMP/NIMP may exist. In these circumstances, local legislation is followed.

All supplies indicated in [Table 2](#) will be provided per the “Sourcing” column depending upon local country operational requirements. If local sourcing, every attempt should be made to source these supplies from a single lot/batch number where possible (eg, not applicable in the case where multiple lots or batches may be required due to the length of the study, etc.).

Refer to Section 8.1.8 for details regarding administration of the study intervention.

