8.4 Adverse Events (AEs), Serious Adverse Events (SAEs), and Other Reportable Safety Events

The definitions of an AE or SAE, as well as the method of recording, evaluating, and assessing causality of AE and SAE and the procedures for completing and transmitting AE, SAE, and other reportable safety event reports can be found in Appendix 3.

Adverse events, SAEs, and other reportable safety events will be reported by the participant (or, when appropriate, by a caregiver, surrogate, or the participant's legally authorized representative).

The investigator and any designees are responsible for detecting, documenting, and reporting events that meet the definition of an AE or SAE as well as other reportable safety events. Investigators remain responsible for following up AEs, SAEs, and other reportable safety events for outcome according to Section 8.4.3.

The investigator, who is a qualified physician, will assess events that meet the definition of an AE or SAE as well as other reportable safety events with respect to seriousness, intensity/toxicity and causality.

8.4.1 Time Period and Frequency for Collecting AE, SAE, and Other Reportable Safety Event Information

All AEs, SAEs, and other reportable safety events that occur after the consent form is signed but before intervention allocation/randomization must be reported by the investigator if the participant is receiving placebo run-in or other run-in treatment, if the event cause the participant to be excluded from the study, or is the result of a protocol-specified intervention, including but not limited to washout or discontinuation of usual therapy, diet, or a procedure.

All AEs from the time of intervention allocation/randomization through 30 days following cessation of study intervention must be reported by the investigator.

All AEs meeting serious criteria, from the time of intervention allocation/randomization through 90 days following cessation of study intervention or 30 days following cessation of study intervention if the participant initiates new anticancer therapy, whichever is earlier, must be reported by the investigator (see Appendix 7 for Germany-specific study requirements).

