9.5.2 Safety Analysis Populations

Safety analyses will be conducted in the All Participants as Treated (APaT) population, which consists of all randomized participants who received at least one dose of study intervention. Participants will be included in the treatment group corresponding to the study intervention they actually received for the analysis of safety data using the APaT population. This will be the treatment group to which they are randomized except for participants who receive incorrect study intervention for the entire treatment period; such participants will be included in the treatment group corresponding to the study intervention actually received. Any participant who receives the incorrect study intervention for one cycle but receives the randomized study intervention for all other cycles, will be analyzed according to the randomized treatment group, and a narrative will be provided for any events that occur during the cycle for which the participant is incorrectly dosed.

At least one laboratory, vital sign, or ECG measurement obtained subsequent to at least one dose of study intervention is required for inclusion in the analysis of the respective safety parameter. To assess change from baseline, a baseline measurement is also required.

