9.6.2 Statistical Methods for Safety Analyses

Safety and tolerability will be assessed by clinical review of all relevant parameters including AEs, laboratory tests, vital signs, and ECG measurements.

Individual events and the broad AE categories consisting of the proportion of participants with any AE, a drug-related AE, a serious AE, an AE which is both drug-related and serious, a Grade 3-5 AE, a drug-related Grade 3-5 AE, a fatal AE, dose interruption due to an AE, discontinuation due to an AE, adverse event of special interest (AEOSI), clinically significant adverse event (CSAE) will be summarized by counts and percentages by treatment group ([Table 9](#)).

Table 9 Analysis Strategy for Safety Parameters

Safety Endpoint	Descriptive Statistics
Any AE	X
Any drug-related AE	X
Any Grade 3-5 AE	X
Any drug-related Grade 3-5 AE	X
Any serious AE	X
Any serious drug-related AE	X
Treatment interruption due to AE	X
Treatment discontinuation due to AE	X
Death	X
Any AEOSI	X
Any CSAE	X
Any Grade 3-5 AEOSI	X
Any Grade 3-5 CSAE	X
Any serious Grade 3-5 AEOSI	X
Any serious Grade 3-5 CSAE	X
Change from baseline results (laboratory test toxicity grade)	X

Abbreviations: AE=adverse event; AEOSI=adverse event of special interest; CSAE=clinically significant adverse event.

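### The end-of-study adverse event tables by arm state no tabulation window, so by default they pool the blinded lenvatinib/placebo period with the later open-label, pembrolizumab-only period

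*Protocol*

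**What the plan says.** Protocol Section 9 explains that Amendment 011-03 was implemented to unblind the study and "remove lenvatinib and matching placebo from the treatment arms". The Synopsis adds: "All participants remaining in the study will receive open-label pembrolizumab only". Section 6.1 agrees: "As of Amendment 011-03, only pembrolizumab will be administered".

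Efficacy and patient-reported analyses then stop, and Section 9 states: "Selected analyses of safety endpoints will be performed at the end of the study". Under Section 9.6.2, individual events and the AE categories of Table 9 "will be summarized by counts and percentages by treatment group". The population is All Participants as Treated. On the group used, Section 9.5.2 says: "This will be the treatment group to which they are randomized except for participants who receive incorrect study intervention for the entire treatment period".

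On collection, Section 8.4.1 says: "All AEs from the time of intervention allocation/randomization through 30 days following cessation of study intervention must be reported by the investigator". Serious AEs run to 90 days, or 30 days if new anticancer therapy starts (120 days in Germany, Appendix 7). A footnote to the Schedule of Activities dates discontinuation from the stop of all study drug.

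Sections 8.10.3 and 9.6.1 exclude Second Course responses and progressions from the primary efficacy analyses. There is no matching sentence for safety, although the Second Course schedule (1.3.2) includes AE review.

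The supplemental SAP (sSAP 3.6.2) still plans between-arm 95% confidence intervals for Tier 2 events. It also offers an optional exposure adjustment, aimed at unequal follow-up.

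**The concern.** The safety objective in Section 3 contrasts pembrolizumab + lenvatinib with pembrolizumab + placebo. After the switch the two arms receive the same open-label drug. If later AEs enter the by-arm tables, the combination column mixes two treatment periods, and the contrast includes time in which no treatment difference exists.

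The rows on drug-related events raise a second issue. Section 4.2.2 justified the placebo because it "will ensure the objectivity of the local investigators" in treatment decisions and causality assessment. After unblinding that protection is gone. Appendix 3 (10.3.4) also lets investigators revise causality on follow-up, so calls first made blind may change later.

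At stake is how readable the only remaining end-of-study analysis is. No efficacy conclusion and no hypothesis test is affected.

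**Working it through.** The plan gives no figure to reproduce, so the first step is to trace the rules.

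1. **Arm.** A participant whose lenvatinib was stopped under the amendment did not receive incorrect treatment for the whole treatment period, so Section 9.5.2 leaves that participant in the combination group.
2. **Window.** For a participant who continues, study drug ceases at the last pembrolizumab dose, so AEs reach the database until 30 days after that dose, and serious AEs until 90 days.
3. **Split.** Neither Section 9.6.2 nor sSAP 3.6.2 cuts or splits the tables at unblinding or at the last lenvatinib/placebo dose. The optional exposure adjustment counts cycles of study drug (sSAP 3.12), so it does not separate the periods either.

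**How much treated time falls after the switch**

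Inputs:
- Accrual pace: 370 participants in about 20 months (sSAP Table 8), or 18.5 per month. 487 / 18.5 = 26.3, so about 26 months (assumed uniform).
- Gap *m* from the last randomization to the switch: 0 to 4 months (assumed).
- Time on treatment: exponential (assumed), with medians borrowed from progression-free survival: 3.2 months (control, Section 9.9), 3.2 / 0.7 = 4.57 (design hazard ratio), and 5.4 (urothelial cohort of the phase 1b/2 study, Section 2.2.3).

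The share on treatment at the switch, with l = ln 2 / median, is [exp(−l·m) − exp(−l·(m + 26))] / (26·l).

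| Gap *m* | Median 3.2 | Median 4.57 | Median 5.4 |
|---|---|---|---|
| 2 months | 11.5% (56 of 487) | 18.4% | 22.4% |

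At m = 0 the range over these medians is 17.7% to 28.9%; at m = 4 it is 7.4% to 17.3%. The overall range is about 7% to 29%. With exponential durations, this is also the share of on-treatment person-time after the switch. A simulation adding the 35-cycle cap and the 30-day window, with accrual over 22 to 26 months and medians up to 6.5 months, gives 7% to 34% of AE-window person-time.

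**Effect on percentages**

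Table 9 counts participants, so an event after the switch matters only in someone without an earlier one. Let *a* and *b* be the pre-switch incidences, *s* the share still treated, and *c* the later risk in those still event-free. With *s* and *c* equal in both arms and independent of earlier events, each arm becomes a + (1 − a)·s·c, and the difference becomes (a − b)(1 − s·c).

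Take a = 50%, b = 30%, c = 0.5 (all assumed):
- s = 11%: 20 × (1 − 0.055) = 18.9 points
- s = 22%: 20 × (1 − 0.11) = 17.8 points
- Full range, s = 7% and 29%: 20 × 0.965 = 19.3 and 20 × 0.855 = 17.1 points

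If persistence differs by arm, the direction can change. With 22% still treated on the combination and 11% on control, the figures are 55.5% and 33.85%, a difference of 21.65 points.

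**Effect on rates**

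With equal rates after the switch and a constant control rate, a true rate ratio R reads as (1 − s)·R + s. For R = 2.0 this is 1.9, 1.8 and 1.7 at s = 10%, 20% and 30%.

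**The case against.** Several counter-arguments have force.

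- **Collection is not tabulation.** Section 8.4.1 tells investigators what to report. It does not say what Table 9 counts. A reader might infer an explicit rule counting AEs by arm to 30 days after the last pembrolizumab dose; there is none. This stands: pooling is the default reading of a silent plan.
- **An unmixed table may exist.** sSAP 3.4.3 refers to a study report, CSR P011V01MK7902, with a 26-JUL-2021 cutoff, before the Amendment 03 date of 24-SEP-2021. This stands as a possibility, but the documents do not say which safety tables that report holds.
- **Pembrolizumab-only time was always allowed.** Under the original schema (Figure 1), pembrolizumab could continue after lenvatinib or placebo stopped. This stands. What is new is a mandated, unblinded withdrawal for everyone still on lenvatinib/placebo.
- **Safety is descriptive.** Formal comparisons were dropped, and later immune-related AEs are genuine events that must be reported. This limits the consequence and argues for keeping an all-events summary. It does not argue against showing the periods separately.
- **A hard cut could misfile events.** A lenvatinib toxicity starting days after the last dose would land in the pembrolizumab-only table. This stands, and it is why a lag is needed. For the same reason, causality should not be frozen at unblinding, since Appendix 3 permits revision.

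**Conclusion.** The concern holds as a gap in the tabulation rule. Read by default, the end-of-study tables pool the blinded period with the open-label pembrolizumab period, including any Second Course, and pool blinded with unblinded causality calls. The dilution of the descriptive contrast is modest: about 7% to 29% of on-treatment person-time after the switch, and a 20-point difference reading as about 18 to 19 points when 11% to 22% of each arm is still treated. These sizes rest on assumed accrual, switch date, treatment duration and incidences, and on equal persistence in the two arms. The documents fix neither size nor direction.

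Two stronger readings are tempting. One is that the tables no longer describe the combination; on the same assumptions 71% to 93% of treated time precedes the switch. The other is that the combination column absorbs up to 35 + 17 open-label cycles. That would need randomization close to the switch, completion of all 35 cycles, then progression and Second Course entry before Amendment 011-04 closed it. It is an extreme, not a typical, case.

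**What to change.** In Protocol Section 9.6.2 and sSAP 3.6.2:

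- For participants still on lenvatinib/placebo at the Amendment 011-03 switch, limit the by-arm Table 9 summaries to AEs with onset up to the last lenvatinib/placebo dose plus a stated lag (for example the existing 30-day AE and 90-day serious AE windows), or to the end of the usual window if that is earlier.
- Tabulate later AEs, including Second Course, in a separate open-label pembrolizumab table.
- Keep an all-events summary for completeness.
- Flag drug-related calls made or revised after unblinding; do not discard them.
- State whether CSR P011V01MK7902 already provides the pre-switch by-arm safety tables.

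The cost is SAP wording, a date flag on existing AE records, an additional set of AE tables, and slightly fewer events in the by-arm table. No new data are needed. The change does not address pembrolizumab-only time after individual lenvatinib discontinuation before the switch, which belonged to the original design.
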